8.4.4 Safety Analyses

Adverse events will be coded as per the CTCAE v4.0. Each AE will be coded once for each patient based on the maximum severity during the assessment period. The relationship of AEs to study intervention will be recorded in addition to the onset date, end date, severity, expectedness, and outcome.

Dose-limiting toxicities are defined as follows (during treatment and within the first three weeks after treatment):

- Grade 3 rectal, small bowel, or urinary toxicity that does not resolve to Grade 2 or less within 4 days with medical management
- Other grade 3 in-field toxicities attributable to radiation that do not resolve to Grade 2 or less within 4 days with medical management
- Delays of more than one week in completing radiation treatment due to toxicity (cumulative duration of delay over the course of the entire treatment).

Additionally, toxicities attributable to radiation after the DLT assessment period (3 weeks after radiation is completed) will be followed and scored but will not be used for escalation with the following exception. If Grade ≥ 4 late bowel or bladder injury (late toxicity is defined as occurring >90 days after completion of radiotherapy) is observed in 2 patients in any Dose level group, dose escalation will be terminated and the dose below that dose level in which the toxicity was observed will be considered the MTD. Early and late toxicities used for assessment of DLTs should be attributable (possible, probable or definite) to radiation. Sexual and erectile dysfunction as a result of radiation will not be considered a DLT. Note that MTD will be determined for each Group separately.

Dose-limiting toxicities are defined as per section **3.1.1**.

8.4.5 Exploratory Analyses

- Evaluate decision regret at the time of enrollment and at the end of follow up relating to the primary treatment for prostate cancer to determine if successful salvage mitigates decision regret. The percentage of patients scored as having decision regret will be compared to the percentage of patients not exhibiting decision regret (regarding the initial surgery). It is hypothesized the effective salvage therapy will mitigate decision regret expressed at the time of enrollment.
- Explore candidate biomarkers of radiation toxicity in blood and urine of patients receiving image-guided, hypofractionated, focally dose escalated post-prostatectomy radiation. Protein and metabolic biomarkers will be assessed in collected specimens.
- Explore MRI imaging parameters of erectile tissues in regards to testosterone and erectile dysfunction. MRI imaging of erectile tissue will be compared to evaluate for changes in volume and tissue characteristics after radiotherapy.
- To compare dosimetry of standard compared to biological optimization algorithms for treatment planning of post-prostatectomy radiation. Treatment planning will be optimized

with both approaches to allow comparison of normal tissue complication probability curves. Results will be reported in a descriptive fashion.

9 HUMAN SUBJECTS PROTECTIONS

9.1 RATIONALE FOR SUBJECT SELECTION

Subjects from all racial/ethnic groups are eligible for this study if they meet the eligibility criteria. To date, there is no information that suggests that differences in disease response would be expected in one group compared with another. Efforts will be made to extend accrual to a representative population. If differences in outcome that correlate with ethnic identity are noted, accrual may be expanded or a follow-up study may be written to investigate those differences more fully.

9.2 INCLUSION OF WOMEN AND MINORS

Women are excluded from this trial as prostate cancer does not occur in females. Boys younger than 18 are excluded because they do not develop prostate cancer with the exception of rare histologies, such as rhabdomyosarcoma, for which radiation alone and the radiation doses chosen here are not an appropriate treatment.

9.3 EVALUATION OF BENEFITS AND RISKS/DISCOMFORTS

9.3.1 Benefits

The potential benefits of trial participation relate to potential curative treatment of recurrent prostate cancer. As information is gathered from this trial, clinical results will be shared with patients as they become available. Laboratory and clinical data will be frequently gathered and any new significant finding(s) found during the course of the research, which may affect a patient's willingness to participate further, will be explained.

Confidentiality of information concerning participants will be maintained, including in all publications and presentations resulting from this study. Names of participants and/or material identifying participants will not be released without permission, except as such release is required by law. Records at the National Cancer Institute are maintained according to current legal requirements, and are made available for review, as required by the Food and Drug Administration or other authorized users, only under the guidelines established by the Federal Privacy Act.

9.3.2 Risks

9.3.2.1 Radiation Therapy

The risks of participation are primarily those of toxicity from irradiation. Subjects in cohort 1 will be exposed to up to 60.4 Gy of radiation in 20 treatment sessions, or up to 54.6 Gy in 15 sessions or up to 47.1 Gy in 10 sessions. Subjects in cohort 2 will be exposed to up to 56.4 Gy in 20 treatment sessions, or 51.2 Gy in 15 sessions, or 44.2 Gy in 10 sessions.

The available studies support that hypofractionated radiation can be safe and effective in this setting. Based on the experience of standard post-prostatectomy radiation, there is a moderate risk of low grade, chronic bowel or bladder toxicity and a decline in erectile function. There is a small risk of more severe injury to the bowel or bladder that could require a procedure (cystoscopy, endoscopy) for evaluation or treatment. Although extremely rare, patients receiving

post-prostatectomy radiation may have severe toxicity that could cause urinary obstruction, worsen post-surgical urinary incontinence, or require surgical correction. It is anticipated that the risks of this schedule of irradiation will be similar although they may be more or less in frequency or intensity. In addition, there smaller risks from blood draw, such as the risk of pain, infection or bleeding.

9.3.2.2 Research Blood Collection Risks

Risks of blood draws include pain and bruising in the area where the needle is placed, lightheadedness, and rarely, fainting. When large amounts of blood are collected, low red blood cell count (anemia) can develop. Up to 62 mL of blood may be collected at baseline and up to 52 mL during each follow up visits.

9.3.2.3 MRI risks

The risks associated with MRI are discomfort and claustrophobia.

9.3.2.4 Gadolinium Risks

The most common side effects include injection site pain, nausea, itching, rash, headaches and dizziness. Serious but rare side effects such as gadolinium toxicity and nephrogenic systemic fibrosis, or NSF, are most often seen in patients with severe kidney problems.

9.3.2.5 Other Risks

Risks include the possible occurrence of any of a range of side effects which are listed in the Consent Document or this protocol document. Frequent monitoring for adverse effects will help to minimize the risks associated with administration of the study agents.

9.3.2.6 Non-Physical Risks of Genetic Research

Risk of receiving unwanted information.

Anxiety and stress may arise as a result of the anticipation that unwanted information regarding disease related DNA sequencing or disease tendencies, or misattributed paternity. Patients will be clearly informed that the data related to DNA sequencing and genetic analysis is coded, investigational and will not be shared with patients, family members or health care providers.

Risk related to possibility that information may be released.

This includes the risk that data related to genotype, DNA sequencing or risk for disease tendency or trait can be released to members of the public, insurers, employers, or law enforcement agencies. Although there are no plans to release results to the patients, family members or health care providers, this risk will be included in the informed consent document.

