5.3.3 Management of Results

We plan to contact participants if a clinically actionable gene variant is discovered. Clinically actionable findings for the purpose of this study are defined as disorders appearing in the American College of Medical Genetics and Genomics recommendations for the return of secondary findings that is current at the time of primary analysis. (A list of current guidelines is maintained on the CCR intranet:

<https://ccrod.cancer.gov/confluence/display/CCRCRO/Incidental+Findings+Lists>). Unless requested otherwise, participants will be contacted at this time with a request to provide a sample to be sent to a CLIA certified laboratory.

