5.3.4 Genetic counseling

If the research findings are verified in the CLIA certified lab, the participant will be offered the opportunity to schedule a visit, in person (at our expense) or via telemedicine on an NIH approved platform to have genetic education and counseling with the NCI Genetics Branch to explain this result. If the subject does not want to come to NIH, a referral to a local genetic healthcare provider will be provided (at participant's expense).

This is the only time during the course of the study that secondary findings will be returned. No interrogations regarding clinically actionable findings will be made after the primary analysis.

Participants will be requested to maintain up to date contact information to enable future contact.

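### Section 9.3.2.6 rules out releasing genetic results to patients, while sections 5.3.3 and 5.3.4 plan to contact participants about actionable variants and return verified findings

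*Combined protocol and SAP*

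**What the plan says.** Section 9.3.2.6 of the protocol covers the non-physical risks of genetic research in two parts.

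- Under the risk of unwanted information, it directs what participants are told: "Patients will be clearly informed that the data related to DNA sequencing and genetic analysis is coded, investigational", and that the data "will not be shared with patients, family members or health care providers".
- Under the risk that information gets out, it says that "there are no plans to release results to the patients, family members or health care providers", and adds that "this risk will be included in the informed consent document".

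Neither part has an exception or a cross-reference.

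Section 5.3.3 describes how results are managed: "We plan to contact participants if a clinically actionable gene variant is discovered". It defines actionable by reference to the professional list of secondary findings in force at the time of the primary analysis. Contact is the default: "Unless requested otherwise, participants will be contacted at this time with a request to provide a sample", which goes to a CLIA certified laboratory.

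Section 5.3.4 continues: "If the research findings are verified in the CLIA certified lab, the participant will be offered the opportunity to schedule a visit", in person or by telemedicine, for "genetic education and counseling with the NCI Genetics Branch to explain this result". A participant who does not want to come to NIH is referred to a local genetic provider. The section calls this the one occasion in the study on which secondary findings are returned, and asks participants to keep their contact details current.

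**The concern.** One section denies a plan that another section lays out step by step. Section 9.3.2.6 is also more than background, because it directs what patients are told and names the consent document as the place for the release risk. Staff who followed it literally would give participants an assurance that 5.3.3 and 5.3.4 do not keep.

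The stake is participant protection. Under 5.3.3 a participant who does not want such information has to ask not to be contacted. Someone told that nothing will be shared has little reason to ask. The part of 9.3.2.6 on unwanted information also omits the one planned route by which such information could reach the participant.

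**Working it through.** No arithmetic bears on the conflict. The check is a side-by-side reading of the current text (version dated 06/03/2024).

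| Question | Section 9.3.2.6 | Sections 5.3.3 and 5.3.4 |
|---|---|---|
| Is there a plan to give patients genetic results? | No | Yes, for clinically actionable variants verified in a CLIA certified laboratory |
| Does the study start the contact? | Not mentioned | Yes, unless the participant asks otherwise |
| What starts it? | Not mentioned | The research finding, before verification |
| What follows verification? | Not mentioned | An offer of counseling to explain the result, or referral to a local provider |
| Is an exception or cross-reference given? | None | None |

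**Statement 1, no plans to release results.** The statement speaks of results in general and is not limited to unverified or coded data. Section 5.3.4 says that secondary findings are returned. Both cannot be true as written, so the conflict is direct.

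**Statement 2, patients told that data will not be shared.** The sentence describes the data as coded and investigational. The first contact under 5.3.3 is a request for a new sample, and 5.3.4 explains a result only after verification. The sentence can therefore be read as covering coded research data only, with the verified result outside it. On that reading the conflict is weaker, but it does not disappear. The sample request is made because a research finding exists, so the request itself signals a suspected variant, and nothing in 9.3.2.6 points the reader to 5.3.3 or 5.3.4.

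**Extent.** The statements are addressed to every participant. Section 8.2 puts enrolment at 2 per arm × 2 arms = 4 at the least and 24 per arm × 2 arms = 48 at the most. The 24 per arm agrees with section 3.1.2: 3 dose levels × 6 patients + 6 expansion patients = 24. This range is enrolment only. It does not measure how many would be contacted, which the documents give no way to derive. Three features limit that number:

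- The circulating DNA work is an exploratory feasibility analysis of copy number (5.3.1.2).
- Tumor sequencing depends on available tissue and may be done only if the circulating DNA or exosome results are promising (5.3.1.1).
- Findings are returned on one occasion only (5.3.4).

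**The case against.** The best defence has four parts.

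1. **The no-release clause is subordinate.** It sits in a paragraph about leakage to the public, insurers, employers and law enforcement, and that paragraph promises only that the release risk will appear in the consent document. The sentence that does direct what patients hear is the one where the conflict is weaker. This is fair, and it limits how much can be rested on either statement alone. It does not make the clause true.

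2. **Other text points to a reconciliation.** Section 9.3.1 says that clinical results are shared with patients as they become available, and that significant new findings bearing on willingness to take part are explained. Together with the coded-data reading, this gives some support for separating research data from verified clinical results. But 9.3.1 is a general statement that does not mention genetic findings, and 9.3.2.6 does not draw the distinction.

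3. **The operating procedure is clear.** Sections 5.3.3 and 5.3.4 define what is actionable, provide an opt-out, and require verification before a result is explained. This stands, and it is why those sections should stay and 9.3.2.6 should change.

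4. **Harm is not shown.** A reader might infer that participants have been misinformed at consent. The documents do not support that. The consent form is not among them, an investigator explains procedures and tests in person or remotely (9.4), and the request for current contact details (5.3.4) may itself alert participants to possible contact. The effect on use of the opt-out is likewise an inference that depends on what participants are actually told.

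**Conclusion.** The inconsistency is real and should be corrected. The no-release statement in 9.3.2.6 contradicts 5.3.3 and 5.3.4 outright. The no-sharing statement is defensible on a narrow reading but incomplete, because it has no exception.

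The point is confined to two statements in one risk section. It rests on the current wording alone and on no numerical assumption. Its practical reach depends on two things the documents do not show: what the consent form says, and how many participants would have an actionable variant. No estimate of either is offered, and the enrolment range should not be read as one. The MTD, the DLT rules, the sample size and every planned analysis are unaffected.

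**What to change.** Keep 5.3.3 and 5.3.4 as they are. Add the same clause to both statements in 9.3.2.6:

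> except that, as described in 5.3.3-5.3.4, participants will be contacted, unless they request otherwise, if a clinically actionable variant is found, and a CLIA-verified result will be returned with genetic counseling or referral

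The clause should say that participants will be contacted, not that they may be, because 5.3.3 makes contact the default. It should not limit return to the participant alone, because 5.3.4 allows referral to a local genetic provider and states no such limit.

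Then compare the consent form with the amended text. If the form already describes contact and return, nothing more is needed. Only if it does not, correct it with IRB approval and obtain the IRB determination on new consent that the Statement of Compliance provides for.

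The cost is a minor amendment, which the Statement of Compliance requires the IRB to review and approve before it is implemented, plus the consent form check. Study procedures, sample size and analyses do not change.

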9.4 CONSENT PROCESS AND DOCUMENTATION

The informed consent document will be provided as a physical or electronic document to the participant as applicable for review prior to consenting. A designated study investigator will carefully explain the procedures and tests involved in this study, and the associated risks, discomforts and benefits. In order to minimize potential coercion, as much time as is needed to review the document will be given, including an opportunity to discuss it with friends, family members and/or other advisors, and to ask questions of any designated study investigator. A signed informed consent document will be obtained prior to entry onto the study.

Abbreviated Title: Image guided radiation

Version Date: 06/03/2024

The initial consent process as well as re-consent, when required, may take place in person or remotely (e.g., via telephone or other NIH approved remote platforms used in compliance with policy, including HRPP Policy 303) per discretion of the designated study investigator and with the agreement of the participant. Whether in person or remote, the privacy of the subject will be maintained. Consenting investigators (and participant, when in person) will be located in a private area (e.g., clinic consult room). When consent is conducted remotely, the participant will be informed of the private nature of the discussion and will be encouraged to relocate to a more private setting if needed.

Consent will be documented with required signatures on the physical document (which includes the printout of an electronic document sent to participant) or as described below, with a manual (non-electronic) signature on the electronic document. When required, witness signature will be obtained similarly as described for the investigator and participant.

Manual (non-electronic) signature on electronic document:

When a manual signature on an electronic document is used for the documentation of consent at the NIH Clinical Center, this study will use the following to obtain the required signatures:

- Adobe platform (which is not 21 CFR Part 11 compliant); or,
- iMedConsent platform (which is 21 CFR Part 11 compliant)

During the consent process, participants and investigators will view individual copies of the approved consent document on screens at their respective locations (if remote consent); the same screen may be used when in the same location but is not required.

Both the investigator and the participant will sign the document using a finger, stylus or mouse.

Note: Refer to the CCR SOP PM-2, Obtaining and Documenting the Informed Consent Process for additional information (e.g., verification of participant identity when obtaining consent remotely) found at:

<https://ccrod.cancer.gov/confluence/pages/viewpage.action?pageId=73203825>.

10 REGULATORY AND OPERATIONAL CONSIDERATIONS

10.1 STUDY DISCONTINUATION AND CLOSURE

This study may be temporarily suspended or prematurely terminated if there is sufficient reasonable cause. Written notification, documenting the reason for study suspension or termination, will be provided by the suspending or terminating party to study participants, investigator, and regulatory authorities. If the study is prematurely terminated or suspended, the Principal Investigator (PI) will promptly inform study participants, the Institutional Review Board (IRB), and sponsor and will provide the reason(s) for the termination or suspension. Study participants will be contacted, as applicable, and be informed of changes to study visit schedule.

Circumstances that may warrant termination or suspension include, but are not limited to:

- Determination of unexpected, significant, or unacceptable risk to participants
- Insufficient compliance to protocol requirements
- Data that are not sufficiently complete and/or evaluable
- Determination that the primary endpoint has been met
- Determination of futility

Abbreviated Title: Image guided radiation

Version Date: 06/03/2024

Study may resume once concerns about safety, protocol compliance, and data quality are addressed, and satisfy the sponsor, IRB and as applicable, Food and Drug Administration (FDA).

10.2 QUALITY ASSURANCE AND QUALITY CONTROL

The clinical site will perform internal quality management of study conduct, data and biological specimen collection, documentation and completion. An individualized quality management plan will be developed to describe a site's quality management.

Quality control (QC) procedures will be implemented beginning with the data entry system and data QC checks that will be run on the database will be generated. Any missing data or data anomalies will be communicated to the site(s) for clarification/resolution.

Following written Standard Operating Procedures (SOPs), the monitors will verify that the clinical trial is conducted and data are generated and biological specimens are collected, documented (recorded), and reported in compliance with the protocol, International Council for Harmonisation Good Clinical Practice (ICH GCP), and applicable regulatory requirements (e.g., Good Laboratory Practices (GLP), Good Manufacturing Practices (GMP)).

The investigational site will provide direct access to all trial related sites, source data/documents, and reports for the purpose of monitoring and auditing by the sponsor, and inspection by local and regulatory authorities.

10.3 CONFLICT OF INTEREST POLICY

The independence of this study from any actual or perceived influence, such as by the pharmaceutical industry, is critical. Therefore, any actual conflict of interest of persons who have a role in the design, conduct, analysis, publication, or any aspect of this trial will be disclosed and managed. Furthermore, persons who have a perceived conflict of interest will be required to have such conflicts managed in a way that is appropriate to their participation in the design and conduct of this trial. The study leadership in conjunction with the National Cancer Institute has established policies and procedures for all study group members to disclose all conflicts of interest and will establish a mechanism for the management of all reported dualities of interest.

